### **6.12.2. Analysis of NfL**

To evaluate the change from baseline in neurofilament light chain (NfL) concentrations, an MMRM analysis will be used to compare change from baseline between treatments up to 104 weeks of treatment in the Evaluable Efficacy dataset. All NfL values will be log transformed

prior to calculating baseline and change values. The model will include the fixed, categorical effects of treatment, visit, sex, and treatment-by-visit interaction, as well as continuous effects of log baseline, age, and log baseline-by-treatment interaction. Visit will be considered a categorical variable with values equal to the visit numbers at which NfL is assessed. The null hypothesis is that the difference in LSM between the LY3303560 dose groups and placebo equals zero.

### **6.12.3. Analysis of Plasma Tau**

To evaluate the change from baseline in plasma tau concentrations (total tau and phospho tau 181), an MMRM analysis will be used to compare change from baseline between treatments up to 104 weeks of treatment in the Evaluable Efficacy dataset. All plasma tau values will be log transformed prior to calculating baseline and change values. The model will include the fixed, categorical effects of treatment, visit, sex, and treatment-by-visit interaction, as well as continuous effects of log baseline, age, and log baseline-by-treatment interaction. Visit will be considered a categorical variable with values equal to the visit numbers at which tau is assessed. The null hypothesis is that the difference in LSM between the LY3303560 dose groups and placebo equals zero.

### **6.12.4. Analysis of vMRI**

Analyses of the following volumetric MRI (vMRI) parameters will be conducted (right + left for all but whole brain volume and ventricular volume):

- Hippocampal volume (cm^3)
- Entorhinal cortex (cm^3)
- Inferior parietal lobe (cm^3)
- Isthmus cingulate (cm^3)
- Lateral parietal lobe (cm^3)
- Medial temporal lobe (cm^3)
- Precuneus (cm^3)
- Prefrontal lobe (cm^3)
- Superior temporal lobe (cm^3)
- Cortical (cm^3)
- Whole temporal lobe (cm^3)
- Atrophy of total whole brain volume (cm^3)
- Enlargement of Ventricular volume (cm^3)
- White Matter (cm^3)
- White Matter Hypo Intensities (cm^3)

All of the above volumes are corrected for intracranial volume. To evaluate the changes in vMRI data after treatment, an MMRM analysis will be used to compare change from baseline to 104 weeks in the Evaluable Efficacy dataset. The change from baseline to the endpoint visit will be the dependent variable. The model will include the fixed, categorical effects of treatment, visit, and treatment-by-visit interaction, as well as continuous effects of baseline vMRI, baseline intracranial volume (ICV) and age. The null hypothesis is that the difference in LSM between the

LY3303560 active dose groups and placebo equal zero. A similar analysis will be performed for completers.

To assess the relationship of vMRI with cognition and function with treatment, Spearman's rank correlation coefficient will be obtained on change from baseline to Week 104 for vMRI parameters with change from baseline to Week 104 for iADRS, ADAS-Cog13, ADCS-ADL, MMSE, and CDR-SB; this will be performed using all patients who have the clinical outcome and vMRI result at Week 104; adjusted for age, baseline intracranial volume (ICV), and sex; and include patients from both treatment groups.

## 6.13. Safety Analyses

### 6.13.1. Extent of Exposure

Maximum days of exposure will be calculated for each patient (date of last dose – date of first dose +1). Accounting for missed infusions, minimum days of exposure will be collected for each patient (number of infusions\*28). Summary statistics will be provided for the total number of days and patient-years of exposure by treatment. Additionally, the number of infusions will be summarized by treatment. Study drug treatment assignment will be listed.

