## 5. Study Design

### 5.1. Summary of Study Design

Study LMDC is a multicenter, randomized, double-blind, placebo-controlled, Phase 2 study of LY3303560 in patients with early symptomatic AD and low-to-medium cerebral tau burden. A combination of visual and quantitative assessments of tau PET is used to identify eligible patients:

- Visual assessment of AD+ (increased activity in posterior temporal regions only) AND  $1.10 < \text{SUVR} \leq 1.46$
- Visual assessment of AD++ (increased activity in temporal and parietal regions) AND  $\text{SUVR} \leq 1.46$

The maximum possible duration of the study is 121 weeks that includes a screening period of up to 8 weeks, a treatment period of 100 weeks, a 4-week post last dose assessment, and an immunogenicity and safety follow-up period of up to 13 weeks, following the last dose of the study drug at Week 100. Subjects who meet entry criteria will be randomized in a 1:1:1 ratio to one of the following treatments:

- **1400 mg LY3303560:** LY3303560 1400 mg IV infusion Q4W for 100 weeks (Visit 2 [Week 0] to Visit 27 [Week 100]).
- **5600 mg LY3303560:** LY3303560 5600 mg IV infusion Q4W for 100 weeks (Visit 2 [Week 0] to Visit 27 [Week 100]).
- **Placebo:** IV placebo infusion Q4W for 100 weeks (Visit 2 [Week 0] to Visit 27 [Week 100]).

The first safety review by a Data Monitoring Committee will be conducted after approximately 30 patients have received 3 doses and completed the 4 week assessment period ( i.e. just prior to their 4th dose). Enrolment will halt after these patients have received one dose of study treatment, however those patients already dosed will continue their allocated treatment. If any of these patients discontinue from study treatment for reasons other than safety, they may be replaced, upon discussion between the investigators and Lilly.

The primary hypothesis being tested is that LY3303560 administered for 100 weeks will result in a significant slowing in cognitive/functional decline compared with placebo as measured by the change from baseline to the end of the double-blind period (Week 104) on the integrated Alzheimer's Disease Rating Scale (iADRS), in subjects with early symptomatic AD (where early symptomatic AD refers to the combination of 2 stages: prodromal AD [mild cognitive impairment (MCI)-AD] and mild dementia due to AD; Alaka et al. 2015) who have low-to-medium tau burden.

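### SAP 6.13.1 gives the last infusion 28 days in the minimum exposure but 1 day in the maximum, so the minimum exceeds the maximum by about 27 days for patients dosed near schedule with no missed infusion

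*SAP*

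**What the plan says.** Section 6.13.1 of the SAP sets out two measures of days on treatment for each patient:

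- Upper measure: "Maximum days of exposure will be calculated for each patient (date of last dose – date of first dose +1").
- Lower measure, meant to allow for missed infusions: "minimum days of exposure will be collected for each patient (number of infusions\*28").

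Total days and patient-years are then summarised by treatment, and the number of infusions is summarised separately. The section does not say which measure feeds the patient-years, and it does not cap the lower measure at the upper one.

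The schedule is in section 5.1. The 1400 mg arm is described as "LY3303560 1400 mg IV infusion Q4W for 100 weeks (Visit 2 [Week 0] to Visit 27 [Week 100"]), and the 5600 mg and placebo arms have the same timing. The safety follow-up is described as "following the last dose of the study drug at Week 100".

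Sections 5.4 and 6.16.1 describe the first interim safety review. They equate three months of exposure with having completed the four weeks that follow the third dose. An exposure summary is listed for the first interim review (6.16.1), carried into the second (6.16.2) and listed again for the third (6.16.3).

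**The concern.** A minimum and a maximum should bracket the quantity of interest and should meet when there is nothing to be uncertain about. Here the uncertainty comes from missed infusions, so the two should coincide in a patient who missed none. Instead they cross in exactly that patient, because the two formulas treat the interval after the last infusion differently.

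What is at stake is the exposure table in the study report and the corresponding summaries given to the data monitoring committee. A reader would find a minimum larger than the maximum in the most compliant patients. Patient-years would also depend on a choice of measure that the SAP leaves open. In proportion, the gap is largest for short exposure, so the first interim summary and early discontinuers are affected most.

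**Working it through.** The SAP states no exposure total to reproduce, so the check applies its formulas to its own schedule.

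**Inputs**

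- Dosing every 28 days, Week 0 to Week 100, Visits 2 to 27 (section 5.1).
- Number of infusions: 100/4 + 1 = 26, which matches 27 − 2 + 1 = 26 visits.
- First to last dose: 100 × 7 = 700 days.
- Maximum = last − first + 1; minimum = infusions × 28 (section 6.13.1).

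**General result.** For k consecutive on-schedule infusions, maximum = 28(k − 1) + 1 and minimum = 28k. The difference is 28k − 28(k − 1) − 1 = 27 days for every k.

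| Consecutive infusions, none missed | Maximum (days) | Minimum (days) | Minimum − maximum |
|---|---|---|---|
| 1 | 1 | 28 | 27 |
| 3 | 57 | 84 | 27 |
| 6 | 141 | 168 | 27 |
| 13 | 337 | 364 | 27 |
| 26 | 701 | 728 | 27 |

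In patient-years, a completer has 701/365.25 = 1.92 as maximum and 728/365.25 = 1.99 as minimum. The maximum is below the minimum by 27/728 = 3.7% for a completer, 27/84 = 32% after three doses, and 27/28 = 96% after one dose.

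**Missed infusions.** With the first and last doses on schedule and infusions missed in between, the maximum stays at 701. One missed infusion gives a minimum of 25 × 28 = 700, so the order is restored by one day. Two give 24 × 28 = 672.

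**Off-schedule dates.** If the span from first to last dose runs d days over 700, a patient with all 26 infusions has maximum 701 + d and minimum 728. The minimum is larger whenever d is below 27. At d = 27 the two are equal at 728.

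**The SAP's own convention.** Three doses fall at Weeks 0, 4 and 8. Four weeks after the third is Week 12, or 84 days. That equals infusions × 28 (3 × 28 = 84), not the maximum formula (56 + 1 = 57).

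**Check of the remedy.** With maximum = last − first + 28:

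- All 26 infusions on schedule: 700 + 28 = 728 against 728.
- One interior miss: 728 against 700. Two: 728 against 672.
- A single infusion: 28 against 28.
- All 26 infusions, last dose 3 days early: 697 + 28 = 725 against 728. The order is still reversed unless the minimum is capped at the maximum.

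**The case against.** The strongest reply is that last dose minus first dose plus 1 is a valid measure of dosing duration, and that calling it too short assumes exposure lasts a further 28 days. The first half stands: as a dosing-duration measure the formula is sound. It fails only as an upper bound beside a minimum that does credit those 28 days. The second half does not stand, because the SAP itself counts exposure to four weeks after the last dose at the first interim review.

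Some stronger readings are tempting, and the document does not support them.

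- *That safety conclusions are distorted because patient-years are the denominator.* Sections 6.13.2 to 6.13.6 and 6.13.9 compare adverse events, laboratory, vital sign and ECG abnormalities and suicidality outcomes mainly by numbers and proportions of patients, or by mean change. Section 6.18 reports participants at risk. No exposure-adjusted rate is planned.
- *That the arms are biased against each other.* All three share one schedule, and for on-schedule patients the gap is the same 27 days in each. Proportional effects could differ if early stopping differed by arm, but nothing in the SAP shows this.
- *That every fully dosed patient is affected.* A first-to-last-dose span at least 27 days over nominal removes the inversion. The SAP gives no visit windows, and section 6.1.1 anticipates out-of-window visits during the pandemic.

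It is also fair to say that the infusion count, reported separately, is unaffected and gives the reader one unambiguous measure. Another consistent repair exists: a minimum of (infusions − 1) × 28 + 1, which gives 25 × 28 + 1 = 701 for both measures in an on-schedule completer. It would, however, depart from the interim-review convention.

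**Conclusion.** The point holds, within descriptive exposure reporting only. The two definitions in section 6.13.1 contradict each other for patients dosed near schedule with no missed infusion, whether they complete or stop early. Nothing elsewhere in the SAP reconciles them. The inversion is 27 days on nominal dates. For a patient with all 26 infusions it is 27 − d days when the dosing span runs d days over nominal, and it is gone once d reaches 27.

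The conclusion assumes a 28-day interval and the Week 0 to Week 100 schedule in section 5.1. How many patients fall in the affected group cannot be known from the SAP. The infusion counts, the planned adverse event comparisons and the efficacy analyses are untouched. It is worth correcting because the error is certain, it reaches both the final and the committee outputs, and it is cheap to remove.

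**What to change.** Amend section 6.13.1 in three respects:

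1. Define maximum exposure as last dose date − first dose date + 28, in line with how sections 5.4 and 6.16.1 count exposure at the first interim review.
2. Keep minimum exposure as infusions × 28, capped at that patient's maximum, so that slightly early visits cannot reverse the order.
3. State which of the two measures feeds patient-years.

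The cost is a few words in the SAP and a small change to the exposure derivation. No new data are needed, and no dosing or clinical rule is touched. If exposure tables have already gone to the data monitoring committee under the present wording, a note describing the change in definition would be enough.

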### 6.13.2. Adverse Events

Treatment-emergent adverse events (TEAEs) will be defined as events that first occurred or worsened after the randomization date (Visit 2 date). Should there be insufficient data for AE start date, stop date, and time to make this comparison, the AE will be considered a post-baseline event and eligible for being treatment-emergent. The MedDRA lower-level term (LLT) will be used in the treatment-emergent computation. The maximum severity for each lower-level term (LLT) during the baseline period will be used as baseline.

An overview of AEs, including the number and percentage of patients who died, suffered serious adverse events (SAEs), discontinued due to AEs and who suffered TEAEs, will be provided. Comparison between treatments will be performed using Fisher's Exact Test.

Summaries of AEs by decreasing frequency of PT within SOC will be provided for the following:

- Preexisting conditions
- TEAEs
- TEAEs by maximum severity
- TEAEs occurring in greater than or equal to 2% of patients by PT
- Serious adverse events
- Adverse events and death reported as reason for study treatment discontinuation

These summaries will include number and percentages of patients with TEAEs. Treatment comparisons will be carried out using Fisher's Exact Test.

Preexisting conditions, TEAEs, SAEs, and discontinuations due to AEs will be listed.

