### 5.3. Method of Assignment to Treatment

Patients who meet all criteria for enrollment will be assigned a study (patient) number at Visit 1 and randomized to double-blind treatment at Visit 2. Patients will be randomized to LY3303560 or Placebo in a 1:1:1 ratio. Assignment to treatment groups will be determined by a computer-generated random sequence using an interactive web response system (IWRS). For the first, approximately, 30 patients, the IWRS will be programmed to guarantee balance between the arms for the first interim analysis for safety; this is referred to as the burn-in period. After the burn-in period, patient randomization will then follow the dynamic allocation (minimization) method of Pocock and Simon (1975) to balance the treatment arms using investigative site as a factor. This is to ensure balanced patient assignment between treatment arms within each site at the end of the study.

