**Table 6.6.1. Analysis Populations for Study I8G-MC-LMDC**

Population	Description
Entered	All participants who sign informed consent
Randomized	All entered patients who are randomized to study treatment
Evaluable Efficacy	All randomized patients with at least one post-baseline iADRS13 result (protocol refers to this as the Full Analysis Set)
Safety	All randomized participants who take at least 1 dose of double-blind study treatment. Participants will be analyzed according to the actual treatment group received (actual treatment group is defined as the treatment received at Visit 2).
Per-Protocol	All subjects in the Evaluable Efficacy population who also: 
 
signed the inform consent form
 
had an assessment of the primary endpoint at each scheduled visit completed
 
had no violations of inclusion/exclusion criteria
 
had no study dosing algorithm violation (such as if subjects randomized to treatment A were given treatment B or subjects randomized to treatment A never received the assigned study drug)
 
had no unqualified raters and no raters with substantial scoring errors for the primary measure
 
were not considered non-compliant with regard to study drug (a subject is considered non-compliant when missing or incomplete infusions exceed 20%, OR if missed more than 3 consecutive infusions at any point)
 

Completers	All randomized subjects who have treatment disposition status of complete.
------------	--

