## 6.10. Concomitant Therapy

Prior medications are defined as those that stop before randomization (the day prior to the first administration of study drug). Concomitant medications are defined as those being taken on or after randomization (the day prior to the first administration of study drug). A summary of concomitant medications will be presented as frequencies and percentages for each treatment group. Fisher's exact test will be used to test for treatment differences between groups. If the start or stop dates of therapies are missing or partial to the degree that determination cannot be made of whether the therapy is prior or concomitant, the therapy will be deemed concomitant. A summary table will also be provided for concomitant AChEI/memantine medications.

Medications will be coded using the World Health Organization (WHO) drug dictionary. Concomitant medications will be listed.

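### The TEAE definition uses a cut-off after the Visit 2 date with no reference time, so a literal date comparison could omit non-serious events from the first infusion day (minor)

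*SAP*

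**What the plan says.** SAP section 6.13.2 defines TEAEs as "events that first occurred or worsened after the randomization date (Visit 2 date". The cut-off is a calendar date tied to randomization, and the definition does not mention the first infusion.

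The next sentence covers incomplete timing. It opens "Should there be insufficient data for AE start date, stop date, and time to make this comparison" and makes such an event post-baseline and eligible to be treatment-emergent. Severity is judged against a baseline: "The maximum severity for each lower-level term (LLT) during the baseline period will be used as baseline". The section does not say when that period ends.

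On where randomization and the first dose fall:
- Section 5.1, for the lower dose arm: "LY3303560 1400 mg IV infusion Q4W for 100 weeks (Visit 2 [Week 0] to Visit 27 [Week 100". The other two arms have the same visit range.
- Section 5.3: patients are "randomized to double-blind treatment at Visit 2".
- Table 6.6.1, Safety population: "actual treatment group is defined as the treatment received at Visit 2".
- Section 6.10 defines concomitant medications as "those being taken on or after randomization (the day prior to the first administration of study drug", and uses the same gloss on randomization for prior medications.

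On where TEAE status is used: section 6.13.2 summarizes TEAEs and compares arms by Fisher's exact test, and states "Preexisting conditions, TEAEs, SAEs, and discontinuations due to AEs will be listed". Section 6.18 admits a non-serious event to the registry 'Other' category only if it is a TEAE. Serious events enter the registry table whether or not they are TEAEs.

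**The concern.** An event with onset on the Visit 2 date is not, taken literally, after that date. If the first infusion is given that day, an event starting during or after it would be classed as not treatment-emergent. For an intravenous product, the day of the first infusion is one on which infusion-related events would be looked for.

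Section 6.10 points the other way. If randomization precedes dosing by a day, everything on the infusion day is after the cut-off, including events that began before the drug was given. The SAP therefore supports opposite classifications of the same event.

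At stake is the completeness of the final TEAE tables and of the registry 'Other' category for non-serious events on one day. The final listings have the same gap: section 6.13.2 lists preexisting conditions, TEAEs, serious events and discontinuations due to adverse events. An excluded event that was neither serious nor a cause of discontinuation could appear there only as a preexisting condition.

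**Working it through.** The SAP states no figure on this point, so the check sets the sections side by side and applies the rule to specific events.

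**Is the first infusion at Visit 2?** Section 5.1 gives dosing every 4 weeks from Week 0 to Week 100, which is 100/4 + 1 = 26 infusions. Visits 2 to 27 are 27 − 2 + 1 = 26 visits. The counts agree, so the schedule puts the first infusion at Visit 2, the visit at which section 5.3 randomizes. None of these sections says outright that both happen on one calendar day.

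**Applying section 6.13.2.** Take event A, which starts during or after the first infusion on the infusion day, and event B, which starts earlier that day, before the infusion. Both are non-serious, have a complete start date and do not later worsen.

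| Reading | Event A | Event B |
|---|---|---|
| Randomization and infusion on the same day, dates compared | Not a TEAE (onset date equals the cut-off date) | Not a TEAE |
| Same day, dates and times compared, reference at start of infusion | TEAE | Not a TEAE |
| Same day, dates and times compared, reference at randomization | TEAE | TEAE if it starts after randomization |
| Same day, event time missing and time held to be required | Eligible through the default | Eligible through the default |
| Randomization the day before (section 6.10) | TEAE | TEAE |

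Only the first row loses event A. The second and third rows need a reference time that the SAP does not supply. The fourth row depends on treating a missing clock time as insufficient data. A complete start date is enough to make a comparison with a date, so the default need not come into play.

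**What follows in the first row.** Event A is absent from the TEAE summaries, from the Fisher comparisons on TEAEs and from the registry 'Other' category. If the undefined baseline period includes the Visit 2 day, event A could also set the baseline severity for its lower-level term. A recurrence at the same severity after a later infusion might then be neither a first occurrence nor a worsening.

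**What is not affected.** Serious events and discontinuations due to adverse events have their own summaries and listings in section 6.13.2, and section 6.18 takes serious events regardless of TEAE status. Section 6.16.1 includes an adverse event listing at the first DMC review, and section 6.16.2 carries it into the second.

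**The case against.** The strongest reply is that the two sentences of section 6.13.2 should be read together. A date-only comparison would have no use for time, so its mention points to a date-and-time comparison with an inclusive default. On that reading event A is counted, and part of the proposed fix repeats the default. This stands as evidence of intent. It does not settle the rule, because no reference time is named and the literal cut-off can be programmed from dates alone.

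A second reply is that section 6.10 exists to separate prior from concomitant medication and by itself loses no first-infusion event. That is correct. Its relevance is that it leaves open which day the cut-off falls on and, if it holds, brings pre-dose events in.

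A third reply is that the protocol, which is not at hand, may define the baseline period and the order of procedures at Visit 2. That is fair, and the undefined end of the baseline period carries little weight alone.

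A reader might go further and infer that the plan drops first-infusion reactions, or that the DMC could not see them. The documents do not support either. The loss needs both a same-day Visit 2 and a date-only comparison. The second DMC review, which repeats the adverse event listing, comes after approximately all patients have had the opportunity to complete 12 months of exposure (section 5.4), so first-day events would be in that listing whatever their TEAE status.

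**Conclusion.** The point holds as a minor one. The TEAE rule is worded as strictly after a date that may also be the date of the first infusion, and the SAP disagrees with itself on whether it is. The loss is conditional on Visit 2 being a single day and on dates alone being compared. It is then confined to events on that day that are non-serious, do not later worsen and do not lead to discontinuation. If section 6.10 holds, the error is the opposite one: pre-dose events on the infusion day are counted as TEAEs.

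The number of patients affected cannot be derived, because the SAP gives no rate of events on the first infusion day. For the same reason, it would be wrong to infer that a between-arm comparison would change. No claim of the trial depends on these tests.

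**What to change.** In section 6.13.2, define TEAEs as events that first occur or worsen at or after the start of the first infusion, by date and time. State that an event on the first infusion day with no recorded time counts as treatment-emergent unless it is recorded as starting before the infusion. End the adverse event baseline period at the same point. Reconcile the description of the randomization day in section 6.10 with sections 5.1, 5.3 and 6.13.2.

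The cost is a few sentences of SAP text and a one-line program change. The downside is that a few events that began on that day before dosing may be counted as TEAEs, which errs towards reporting.
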